A BEHAVIORAL INTERVENTION WITH FOSTER FAMILIES

NCT Number: In progress of registering

Date of Original Document: January 1, 2022

STUDY PROTOCOL

Purpose and Aims

The purpose of this study is to test the effects of an easily accessible intervention that is unique for including both caregivers and children living in the home. Three aims will be conducted to: (1) establish the feasibility of the technology-based, family-centered intervention; (2) explore in a preliminary manner the effects of the intervention on stress and relational quality outcomes among family member participants; and (3) explore feasibility and preliminary efficacy of the intervention on diurnal salivary cortisol levels within the foster family population.

Design

This study will use a randomized controlled trial design. Randomization will be used to assign participants into the experimental or control group. Blinding of the two groups to participants will not be done. However, the team will blind the statistical analysis to group with the use of a statistician. Families assigned to the control will have the opportunity to participate in the intervention post- data collection and analysis and outside of the research protocol. The intervention was created in partnership and adapted from the Connected Family Series (CFS) by psychologists at the Karyn Purvis Institute of Childhood Development (KPICD). Adaptation is needed as the original intervention was geared toward adoptive families and excluded foster families. This process is currently occurring, but has not been completed. The intervention also needed content specific to fostering children with special needs. Stress and relational quality outcomes among members will be measured using the concepts of family hardiness, preparedness, and relationship development through a self-report questionnaire which include the Family Hardiness Index, the Integrating Foster Children subscale from the Casey Foster Applicant Inventory, and the Sibling Inventory of Behavior respectively.

Study Timeline

The study will span 6 months to 1 year; 1 month for recruitment and collection of baseline data, 2 months for the intervention, 3 months for post intervention data collection and 3 months for data analysis in 2022. Data will be gathered during the spring and summer of 2022 with the weight-listed control group able to participate in the intervention after data collection of the initial trial period. Dissemination of results is expected by 2023.

Sample

The study proposed here will follow rigorous guidelines to recruit and screen participants, in order to aid in the study's reproducibility and appropriate application (Friedman et al., 2015). The defined study population is foster families with both permanent and foster children in the home. Inclusion criteria for the study includes the following: 1) licensed foster families, 2) must have at least 1 permanent child (biological or adopted) living in the home before the foster or newly adopted child entered the home, 3) at least one foster or foster-to-adopt child placed in the home, 4) all participants other than the foster or foster-to-adopt child must have English as their primary language or be proficient in English. Families will be recruited through professional organizations such as the Karyn Purvis Institute of Childhood Development (KPICD), the Utah Foster Care Foundation – an organization responsible for the prelicensure training and continuing education of foster parents in the state of Utah, as well as a foster parent support group social media platforms (letter of support on file with [name]). Eligibility criteria ensures that sibling interactions and how they affect placement stability will be captured.

Sample Size Justification

The total sample size for the study (N=130) of families was estimated for 80% power for t-test and ANOVAS, $\alpha < .05$ using G*Power software. Although the exact effect size of the intervention is unknown, we used results from the randomized control trial by Schoemaker et al.

(2020) in which a video intervention to improve parenting among foster families was used and their effect size of 0.34 for differences of the intervention on parenting sensitivity measures using the adapted Ainsworth scales for sensitivity and non-interference. Consistent with Shoemaker et al., a similar sample size was found to be sufficient to detect significant results for the original Connected Family Series. Collection of salivary cortisol to achieve exploratory aim 3 will be done with a smaller sample size of 40, consistent with previous similar feasibility studies for hypothalamic–pituitary–adrenal (HPA)-axis function (Pace et al., 2021).

Participant Recruitment

Once a family is recruited, they will be connected (within 1 week) with a study team member and screened for inclusion and exclusion criteria via zoom. If appropriate, the family will be enrolled in the study. Information will be given about the study and informed consent will be collected. An independent statistical team will ensure stratified random assignment to study groups.

Human Subjects Protection

Foster families, including parents, biological children, and foster children in the home (age 6 to 18), recruited through a licensing agency (Foster Care Foundation) will take part in an educational training and support network designed to help participants to prepare and thrive while caring for children in the foster care system. Subjects will come in contact with a Trust-Based Relational Intervention (TBRI) trainer and therapist virtually on-line (K. B. Purvis et al., 2013). TBRI education is the current standard for foster parent training for families accepting level III placements. The pediatric population is needed because both the caregivers and the children in the home have an impact on the stability of the placement.

A special and vulnerable population (children) will be involved in order to conduct research that is intended to impact to improve participant lives and by extension, more vulnerable children (i.e., those in foster care) with current great need relative to risks that are comparably minimal. Online platforms, particularly those that are intended to facilitate effective parenting of children with special needs, hold promise for strengthening current training programs (Kaasbøll et al., 2019). Including children is likely to increase the success of parental trainings. Without studying the family as a whole, we lose the family-centered potential to improve long-term outcomes for foster children. We also are likely to improve the functioning and mental health of the children who participate in the training/intervention. The proposed research uses a stratified randomization design for children with severe behavioral and developmental disabilities, to ensure that the research is reproducible. The control group (receiving no intervention) will be given the opportunity to participant in the intervention after the initial trial.

Potential Risks

Participants will not be put at financial or physical risk during any phase of the proposed research. Psychological and social risks will be addressed through the use of confidential psychological support and referral to treatment or therapy as needed. Because all participants will be licensed foster families, cost of therapy will be covered under the current program already available to foster families. Participants will continue to receive the standard of care or support available in addition to the intervention. Due to the sensitive information that may arise during the study, legal risks and obligations will be monitored by a data and safety monitoring board, comprised of individuals not directly tied to the study (see below). A report will be given by the PI on a monthly basis to the board. A case worker positioned within the governing

agency will be available via cell phone 24/7 to the PI. If a researcher or therapist encounters a situation that may appear to be a safety or legal risk, they will have 24 hours to notify the PI and caseworker.

Adequacy of Protection Against Risks

Recruitment and Informed Consent

Families will be recruited through social media platforms. The study coordinator will screen interested families. For participants who fit the inclusion criteria, the study coordinator will explain the study and expectations and provide the paperwork for informed consent. Signed consent forms will be locked in a cabinet in the Office of Nursing Research at the University of Arizona.

Protection Against Risk

The identity of participants will remain anonymous and confidential. The following safeguards will be put in place: a) unique identification numbers will be used for computerized data entry, b) data will not be released except in aggregate form, c) agency and names or other identifying variables will be absent from written communication or presentations.

Potential Benefits of the Proposed Research to Humans Subject and Others

The average participant will have a 50% chance of being randomized into the intervention group, but all participants will have the opportunity to eventually participate in the intervention if they so choose. The intervention is aimed at improving family relationships and will provide additional community resources. Foster children will benefit from having foster parents and siblings that better understand how to connect and develop positive relationships with children who may have a background of trauma.

Importance of the Knowledge to be Gained

Findings from this trial will be used to improve the placement stability and health of over 600,000 children in the foster care system every year. Results are expected to help improve the resilience of foster families through education and preparation.

Data and Safety Monitoring

The PI will be responsible for reviewing the feedback from the modules. Each week, a review meeting will be held with the PI and the trained therapist to review any concerns or needs of the participants. The Institutional Review Board (IRB) at the University of Arizona will be used for approval and oversight of the trial. The independent safety auditor will conduct reviews of patient responses and reaction to the intervention. A Data and Safety Monitoring Board (DSMB) will oversee coordination and risks across the different settings. This committee will consist of 4 individuals (the PI, the KPICD licensed therapist, and two dissertation committee members), who will meet on a quarterly basis to review and address any perceived or potential risks as the study progresses.

ClinicalTrials.gov Requirements

This study does not include trials of drugs or biologics nor does it include a trial for a device. However, it will be registered at clinicaltrials.gov.

Instrumentation

Sources of Materials

Research material will be obtained in the form of online surveys and point-of-care saliva collection. Surveys and saliva will be collected before the intervention (T1) and after the intervention (T2). Additional collection at 1-month post intervention (T3) will occur. Surveys include the Sibling Inventory of Behavior (SIB), the Family Hardiness Index (FHI), and a modified version of the Casey Foster Applicant Inventory-Applicant Version. Data gathered will

be coded using a unique identifier for each participant. The name and identifying number will be locked separately from the data with access only available to the primary investigator. Saliva specimens will be collected by the participants with only the identifying number on the tube.

Pre-Intervention Assessment

Participants screened and deemed to fit inclusion and not exclusion criteria will fill out a demographic survey and intent to offer permanency. Families will also be asked their willingness to participate in salivary cortisol collection. Caregivers will complete the three-pronged battery of assessments containing a total of 52 questions with an expected time to complete of 15 to 20 minutes for all questionnaires, which will be formatted into one questionnaire for participants. The three questionnaires include the Family Hardiness Index, the Sibling Inventory of Behavior, and the Modified Casey Applicant Inventory.

Hardiness - Family Hardiness Index (FHI)

Measurements for family hardiness will be done using the Family Hardiness Index (FHI). The FHI instrument is a 20-item Likert-type scale with a 4-point response scale ranging from false to true about the family situation (McCubbin et al., 1987). Higher scores indicate higher family hardiness. Validity and reliability have been established through positive correlations with family function measures, with an Cronbach's alpha coefficient of .82 with test-retest reliability of .86 (McCubbin et al., 1996). Studies have employed the FHI to accurately indicate a hardiness levels within foster families and those raising children with special needs (Hendrix & Ford, 2003; Roberts et al., 2017). See Appendix D: Family Hardiness Index.

Relationship Development - Sibling Inventory of Behavior (SIB)

The Sibling Inventory of Behavior (SIB) was developed to assess sibling relationships between a typically developing sibling and a child with a disability using a 28-item questionnaire (Schaefer, 1981) and will be used here to assess relationship development. The measure assesses four aspects of sibling relationships: kindness (nine items), avoidance (six items), involvement (seven items), and empathy (six items). Validity of the SIB scales was demonstrated using correlational and observational data with Cronbach alphas ranging from .64 to .81 for each item, indicating that these items are closely related and thus internally consistent (Volling & Blandon, 2003). See Appendix E: Sibling Inventory of Behavior.

Family Preparedness - Modified Casey Foster Applicant Inventory

A modified version of the Casey Foster Applicant Inventory-Applicant Version will be used to assess family preparedness, which is a psychometric self-report tool used to assess the potential readiness and ability to foster parent successfully (Buehler et al., 2006). Data from previous studies involving foster parents have shown internal consistency and reliability (ranging from 0.64 to 0.96) (Orme et al., 2007). The *Integrating Foster Children* subscale includes ability to integrate a foster child into a foster family with birth or adopted children (Orme et al., 2006). Questions are based on a Likert scale from 1 (strongly disagree) to 4 (strongly agree). Example statements include, “My children want to have a foster brother or sister” and “My children are able to deal with a foster child with serious problems.” See Appendix F: Casey Foster Applicant Inventory Questionnaire.

Exploratory Objective Biological Measure of Stress – Salivary Cortisol

To measure the exploratory aim for objectively measuring an indicator of family stress and HPA axis function, the psychobiological marker of diurnal salivary cortisol will be tested. Concentration of cortisol in saliva over the course of the day is normally high in the morning,

peaks 30-60 minutes after waking (cortisol awakening response/CAR), and is low at night, indicating healthy hypothalamic-pituitary adrenal (HPA) axis function (Adam et al., 2017). Relative disruptions in diurnal cortisol rhythm (e.g., high bedtime levels, a flatter diurnal slope from waking to bedtime, high overall concentration across the day) have been associated with self-reported stress, as well as other aspects of psychological well-being (e.g., depression)(Adam et al., 2017; Juarez Garcia et al., 2016). This study will employ the same methods and analysis as employed by Pace et al. (2021) and was done with permission.

Salivary Cortisol

Collection of saliva will include two family members: the primary caregiver and the permanent sibling that is closest in age to the foster child. If two permanent children are the same age difference away from the foster child, the permanent sibling with who the foster child interacts with most will be selected. Consent and assent forms will be signed by parent and child. Saliva will be gathered for three consecutive days before the intervention (days 1, 2, and 3) and after the intervention (days 31, 32, and 33); each sampling day, participants will provide a waking, 30 min after waking, and bedtime sample. A two-week window for saliva collection will be allowed depending on when the participating family completes the intervention. Participants passively drool through a straw into a 2mL polypropylene tube and labeled each tube with the time and date. Participants will be instructed not to eat, drink, or brush their teeth 30 minutes before each sample, and to keep completed samples in the refrigerator throughout the study period. Participants will ship saliva samples to the lab and samples will be then stored at -20°C. Saliva samples will be batch assayed in duplicate according to manufacturer instructions for cortisol concentrations using an enzyme immunoassay (EIA) kit (Salimetrics, State College, PA). Inter- and intra-assay coefficients of variability in previous studies by the Pace research team

were 8.16% and 7.74%, respectively. In line with prior work (Zeiders et al., 2014), the following cortisol parameters will be assessed: waking level (Sample 1), bedtime level (Sample 3), the CAR (the difference between Sample 2 – Sample 1), the diurnal slope (the difference between Sample 3 - Sample 1), and the area under the curve (AUC) to assess total cortisol output across the day. AUC will be calculated using the trapezoidal method.

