A BEHAVIORAL INTERVENTION WITH FOSTER FAMILIES

NCT Number: In progress of registering

Date of Original Document: October 25, 2021

STATISTICAL ANALYSIS PLAN

Plan for Data Management/Analysis

Randomization: The central hypothesis will be tested using a randomized controlled trial (RCT) design. The intent of the RCT design is to measure the effectiveness of the intervention and decrease bias through randomization (Montori & Guyatt, 2001). Because severity of disability may affect stress levels in the home, partial stratified randomization for disability severity will be employed. Stratified randomization creates balance between the control and intervention groups. Furthermore, stratification between each group allows for disaggregation of data (Friedman et al., 2015). If the highest-needs children are overrepresented in either the control or intervention groups, inferences could be incorrectly skewed. Families will complete an adapted Autism Behavior Checklist (ABC) before randomization, designed to screen for developmental and behavioral problems in children. The ABC was developed to provide a valid behavior checklist to measure level of behavioral concerns in children with disabilities (Krug, 1980) and has demonstrated intra-rater reliability of $r = 0.87$. Families will be stratified to ensure equal disability severity among groups. The two study groups will include 1) the control group with no intervention and 2) families receiving the intervention. Families will fill out the prescreening tool, be randomly assigned to a group, and receive the survey tools. The same surveys will be collected after the intervention for comparison among groups. Families not assigned to the intervention will be offered the option to receive the intervention after the initial study has concluded. Families participating in the salivary cortisol collection will be randomly chosen from the intervention group.

Statistical analysis will be blinded through use of an independent statistician. STATA statistical software will be used to calculate descriptive statistics, t-tests, correlations, and

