regressions to examine prediction and address the study aims. Consistent with the aims of the study, the primary outcome is to determine the feasibility and effect of the intervention on family hardiness and relationship development, with a secondary outcome of stress levels measured via cortisol levels. We hypothesize that the intervention will improve family hardiness measures and sibling relationships, and that salivary cortisol collection of families participating in the collection of saliva will be feasible within this population. The primary investigator examine potential mediation analysis and multi-level modeling to identify relationships of the concepts and individual characteristics nested within families.

References

Friedman, L. M., Furberg, C. D., DeMets, D. L., Reboussin, D. M., & Granger, C. B. (2015).

Fundamentals of clinical trials (5th ed. 2015 ed.). Cham: Springer International Publishing. <https://doi.org/10.1007/978-3-319-18539-2>

Krug, D. A. (1980). Behavior checklist for identifying severely handicapped individuals with high levels of autistic behavior. *Journal of child psychology and psychiatry*, 21(3), 221-229. <https://doi.org/10.1111/j.1469-7610.1980.tb01797.x>

Montori, V. M., & Guyatt, G. H. (2001). Intention-to-treat principle. *Canadian Medical Association Journal (CMAJ)*, 165(10), 1339-1341.

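### The claimed 80% power at 130 families does not follow from an effect size of 0.34: read as a standardized mean difference, it gives about 49%

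*Protocol*

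**What the plan says.** The protocol's Sample Size Justification reads: "The total sample size for the study (N=130) of families was estimated for 80% power for t-test and ANOVAS", with alpha at .05 and G*Power as the software. It concedes "Although the exact effect size of the intervention is unknown" and borrows from an earlier video-intervention trial in foster families "their effect size of 0.34 for differences of the intervention on parenting sensitivity measures". It adds that a similar sample size had been enough for significant results with the original version of the intervention.

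The section does not give:
- the metric of 0.34
- whether the test is one- or two-sided
- whether post-intervention scores or changes are compared
- the layout of the ANOVAs
- a correlation between time points
- an allowance for attrition

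On allocation, the protocol's section on potential benefits says "The average participant will have a 50% chance of being randomized into the intervention group", and the SAP describes two groups. On analysis, the SAP says "STATA statistical software will be used to calculate descriptive statistics, t-tests, correlations, and" regressions, and "The same surveys will be collected after the intervention for comparison among groups". It also states that "the primary outcome is to determine the feasibility and effect of the intervention on family hardiness and relationship development".

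**The concern.** An effect of about a third of a standard deviation normally needs well over 100 participants per arm for 80% power in a two-group t-test. A total of 130 is about half of that, so the stated power looked too high for the stated effect.

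The power statement is the only formal calculation behind the sample size, and the SAP makes the effect on hardiness and sibling relationships part of the primary outcome. If the figure is wrong in this direction, a non-significant result could be reported as coming from a trial with 80% power for the expected effect, when the chance of detecting that effect was close to one half.

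**Working it through.** **Inputs.** Total 130 families, alpha .05, claimed power 80% and effect size 0.34 (protocol, Sample Size Justification). Two groups (SAP). Equal allocation, so 130 / 2 = 65 per arm (protocol, section on potential benefits). Assumed because not stated: two-sided test, no attrition, no baseline adjustment.

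**Attempt to reproduce 80%, with 0.34 as d.** Noncentral t with df = 2n − 2 = 128 and noncentrality d·√(n/2) = 0.34 × √32.5 = 1.938. The two-sided critical value is 1.979.

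| Reading of 0.34 | Power at 130 | Families for 80% |
|---|---|---|
| d, two-sided | 48.6% | 274 (137 per arm) |
| d, one-sided | 61.1% | 216 (108 per arm) |
| Cohen's f, two-group ANOVA (noncentrality f²N = 0.1156 × 130 = 15.03) | 97.0% | 70 |

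None of these gives 80%. Solving the other way, 65 per arm has 80% power at d = 0.495, and 0.495 / 0.34 = 1.46, so 46% larger than 0.34. At d = 0.50, power is 80.8%. That 130 was derived from a medium effect is an inference; the documents do not say so.

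**What the trial could detect.** If the observed difference were exactly 0.34 SD, t = 1.938 on 128 df and p = .055. The smallest significant difference, and the half-width of the 95% CI, is 1.979 × √(2/65) = 0.347 SD.

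**Analyses that use the repeated measurements, d = 0.34, two-sided.** Write r for the correlation between time points.

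- Change scores: effective d = 0.34 / √(2(1 − r)).
- Baseline adjustment: effective d = 0.34 / √(1 − r²), df = 127.
- Between-group test over three time points: f = d/2 = 0.17, noncentrality f²·N·3 / (1 + 2r).

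| Analysis | r = .5 | r = .7 | r = .86 | r giving 80% |
|---|---|---|---|---|
| Change scores | 48.6% | 70.0% | 95.3% | about .76 |
| Baseline-adjusted | 60.3% | 76.8% | 96.5% | about .73 |
| Three-time-point between-group ANOVA | 65.4% | 57.6% | 52.4% | about .2 |

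Two further routes come near 80%. A group-by-time ANOVA with two time points and f = 0.17 gives 77.7% at r = 0 and reaches 80% at r = .057. Baseline adjustment of the mean of T2 and T3, with equal correlations, has residual variance (1 + r)/2 − r² and gives 78% at r = .5 and 83% at r = .6.

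The documents state no model and no value of r for the power calculation. The nearest figure is the "test-retest reliability of .86" quoted for the Family Hardiness Index. For the Sibling Inventory of Behavior only internal consistency is given.

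**Attrition (assumption).** If 15% or 20% of families give no T2 data, unadjusted power at d = 0.34 falls to 42.5% or 40.4%.

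**The case against.** The strongest reply is that the plan is under-specified rather than wrong. The metric of 0.34 lies in a cited trial that is not available here, and the d and f readings err in opposite directions: on the f reading the trial has more than enough power and the harm described does not arise. The word ANOVAS, with three survey time points, may point to a repeated-measures calculation, and several such calculations reach 80% at plausible correlations. The .86 is a test-retest reliability, not a correlation across a two-month intervention, so it cannot exclude a value near .73. The protocol also cites experience with the original intervention as a second basis for the sample size, and its aims describe the effects as preliminary.

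Much of this stands. The 49% depends on the d reading, .86 should not be used to rule out an adjusted analysis, and the preliminary aims lessen the consequence. But the sentence claims 80% for a t-test as well as for ANOVAS. An unadjusted two-group t-test has no correlation to choose, and its power is 49%, 61% or 97% depending on metric and sidedness. Each rescuing analysis needs inputs the plan does not contain. Earlier significant results with a similar sample do not establish 80% power at 0.34 in this trial.

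**Conclusion.** The statement is wrong as written: 80% power at 130 families does not follow from an effect size of 0.34 for the two-group t-test that the protocol names, whether 0.34 is d or f. On the more natural d reading, with equal allocation, a two-sided 5% test, no attrition and no baseline adjustment, power is 48.6% against the stated 80%, and 80% needs 274 families against 130. The mismatch does not depend on the metric, but its direction does. A baseline-adjusted or change-score analysis could bring power near or above 80%, if the plan adopted one and stated the correlation it assumes.

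**What to change.** First establish and state what 0.34 measures, together with the sidedness, the test to which the power applies and any assumed correlation. Keep 130 families and delete the claim of 80% power at 0.34. If 0.34 is a d and the comparison is an unadjusted one, the replacement could read:

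> Taking 0.34 as d, with 65 families per arm analysed, a two-sided 5% t-test on post-intervention scores has 80% power for d = 0.50 and about 49% power for d = 0.34. Effects are preliminary and will be read from the estimate and its 95% CI (half-width about 0.35 SD).

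If a baseline-adjusted model is made the primary analysis, name it in the SAP and quote its power with the assumed correlation: at d = 0.34, about 60%, 77% and 96% for r = .5, .7 and .86. If 0.34 was not a d, recompute on its own metric. In each case, base the figure on the number of families expected to give T2 data.

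The cost is wording only. On the d reading with an unadjusted test, the stated power becomes less favourable; no extra families or assessments are needed.

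### The before and after saliva waves are neither matched nor adjusted for day of week, which adds noise to the cortisol change and becomes bias if start days cluster

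*Protocol*

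**What the plan says.** The protocol's Salivary Cortisol section sets two waves: "Saliva will be gathered for three consecutive days before the intervention (days 1, 2, and 3) and after the intervention (days 31, 32, and 33". There are three samples per day: waking, 30 minutes later and bedtime. Soon after, the section adds: "A two-week window for saliva collection will be allowed depending on when the participating family completes the intervention". It does not say whether the window runs early, late or both ways. Participants will have "labeled each tube with the time and date", so the weekday and clock time of each sample can be recovered.

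The parameters are waking level, bedtime level, CAR (sample 2 minus sample 1), slope (sample 3 minus sample 1) and trapezoidal AUC. For further methods and analysis, the protocol's section on the exploratory biological measure refers to a cited earlier study.

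The SAP's randomization paragraph says: "Families participating in the salivary cortisol collection will be randomly chosen from the intervention group". The SAP gives no model specific to cortisol. Neither document sets a start weekday, matches weekdays between waves, records school or work days, or adjusts for day type.

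The Study Timeline says "Data will be gathered during the spring and summer of 2022" and allots "2 months for the intervention".

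**The concern.** All five parameters use the waking sample, the bedtime sample or both. If caregivers and school-age children keep different hours, or face different demands, on weekends than on school or work days, a change in the mix of days between waves shows up as a change in cortisol. That such a difference exists is an assumption; the documents do not discuss it.

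Aim 3 includes preliminary efficacy on diurnal cortisol, and the SAP lists cortisol as the secondary outcome. With saliva from the intervention group only, the estimate is a within-person before-after change in a sample of 40. There is no concurrent control change to subtract, so a shift in day mix stays in the estimate.

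**Working it through.** The plan states no figure on this point to reproduce. The check is a calendar count.

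**Inputs.** Blocks of three consecutive days; first days 1 and 31 (Salivary Cortisol section); two-week window, direction unstated. Assumption: weekend means Saturday and Sunday.

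**Step 1: nominal offset.** 31 - 1 = 30 days = 4 × 7 + 2. The second block starts two weekdays later than the first.

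| Baseline start | Weekend days before | Second block starts | Weekend days after | Change |
|---|---|---|---|---|
| Mon | 0 | Wed | 0 | 0 |
| Tue | 0 | Thu | 1 | +1 |
| Wed | 0 | Fri | 2 | +2 |
| Thu | 1 | Sat | 2 | +1 |
| Fri | 2 | Sun | 1 | -1 |
| Sat | 2 | Mon | 0 | -2 |
| Sun | 1 | Tue | 0 | -1 |

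Six of seven start days (86%) change the count. The seven changes sum to 0.

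**Step 2: the window.** The number of start days that change depends on the offset modulo 7: 0 of 7 for remainder 0; 4 of 7 for remainders 1 and 6; 6 of 7 for remainders 2 to 5. For offsets 30 to 44, remainder 2 occurs three times and each other remainder twice. The mismatched combinations are 2×0 + 2×4 + 3×6 + 2×6 + 2×6 + 2×6 + 2×4 = 70 of 15 × 7 = 105, or 66.7%. Other readings, with all combinations equally likely (assumption):

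- 30 to 43 days: 64 of 98 = 65.3%
- 23 to 37 days: 70 of 105 = 66.7%
- 16 to 44 days: 134 of 203 = 66.0%

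The mean change is 0 weekend days in every reading.

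**Step 3: clustered start days.** Mean change at exactly 30 days:

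- Mon-Fri: (0 + 1 + 2 + 1 - 1)/5 = +0.6
- Mon-Wed: (0 + 1 + 2)/3 = +1.0
- Fri/Sat: (-1 - 2)/2 = -1.5

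Averaged over the four window readings, these become +0.26 to +0.28, +0.86 to +0.87, and -1.14 to -1.17.

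**Step 4: effect on the cortisol change.** Let b be the weekend-minus-weekday difference in a parameter, and assume that a wave is summarised by its three-day mean. The spurious change for one person is b × (change in weekend days)/3. At 30 days:

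- Mon-Fri starts give an average of 0.6/3 = 0.2b.
- Fri/Sat starts give -1.5/3 = -0.5b.
- Evenly spread starts give an average of 0. The mean squared change in weekend days is (0 + 1 + 4 + 1 + 1 + 4 + 1)/7 = 12/7, so the added between-person SD is √(12/7)/3 = 0.44b in absolute size.

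The documents give no value for b.

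**Step 5: the remedy.** An offset of a whole number of weeks gives 0 of 7 mismatches. Every window reading contains at least two: 35 and 42 days (30 to 44, or 30 to 43); 28 and 35 (23 to 37); 21, 28, 35 and 42 (16 to 44).

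**The case against.** A reader might infer that the second wave is fixed exactly 30 days after the first, so that six of seven is a property of the plan. The two-week window rules that out: the offset varies, and six of seven describes only the nominal schedule.

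A reader might also infer that the cortisol change is necessarily biased. It is not. The imbalance sums to zero over evenly spread start days, and no text in either document says that starts will cluster. Equally, nothing ensures an even spread, so bias remains possible, in either direction.

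Four further points on the other side:

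- **Size.** Neither document shows that cortisol differs on weekends, so any percentage effect would be imported. This stands, and is why the result is left in terms of b.
- **Already handled.** The cited methods may include a day-type rule, and tube dates permit adjustment afterwards. Both are possible, but neither document plans it, and a date does not show whether that family had school or work that day.
- **A third wave.** The Sources of Materials section mentions collection one month after the intervention, which may include saliva. The Salivary Cortisol section describes two waves only. If SAP sampling applies, a third wave would also lack controls.
- **Importance.** Aim 3 is exploratory, and the SAP's cortisol hypothesis concerns feasibility of collection, which weekday mix does not affect. This lowers the priority. It does not remove the point, because the aim also names preliminary efficacy.

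**Conclusion.** The concern holds in limited form. The two waves are not matched or adjusted for day of week. The weekend count changes for six of seven start days at the nominal offset, and for about 65-67% of combinations across the window if all are equally likely. With evenly spread starts the effect is noise in the within-person change. With clustered starts it is bias, which the intervention-only sampling in the SAP leaves uncorrected. The counts rest only on the calendar and a Saturday-Sunday weekend. The consequence for cortisol rests on an assumed, unquantified weekend difference. This is a worthwhile, inexpensive improvement to an exploratory component, not a flaw that invalidates it.

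A possible move from school term in spring to holidays in summer is a related but separate problem. Matching weekdays does not correct it; a day-type record with adjustment does so only in part.

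**What to change.** - In the Salivary Cortisol section, require each person's post-intervention wave to use the same three weekdays as the baseline wave, that is, an offset of a whole number of weeks chosen inside the window already allowed. State the direction of the window.
- Add a school/work-day tick to the tube label or diary.
- In the SAP, adjust the pre-post cortisol analysis for day type, using that tick and the recorded date and time.

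The cost is a sentence or two in each document and one tick box, with no extra samples. The downside is a shift of a few days in the collection date: up to 3 days either way, or up to 6 days later if the window permits only delay.

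Separately, a post-intervention wave at "after the intervention (days 31, 32, and 33" does not fit an intervention of two months in the Study Timeline if day 1 precedes it. The two sections must be reconciled. The weekday rule applies whatever date results.
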